6.1. Study Intervention(s) Administered

6.1.1. Administration

Qualified and trained investigator site personnel will administer elranatamab to participants by SC injection. Ideally, each injection may be up to 2 mL in volume; however, if the maximum volume allowed per institution's policy is lower than 2 mL, the number of injections may be increased to accommodate this difference in volume and ensure the correct dose is delivered.

Elranatamab should be administered to the abdomen, with preference given to the lower quadrants when possible. Refer to Appendix 9 for details on administration of multiple

injections to the abdomen. Study staff should refer to the IP Manual for specific instructions on the handling, preparation, and administration of study intervention.

Participants will receive elranatamab as a SC injection administered QW on Days 1, 8, 15 and 22 of each 28-day cycle. Elranatamab is also administered on C1D4. A minimum of 2 days should be maintained between the 2 step-up priming doses (C1D1 and C1D4), a minimum of 3 days between C1D4 dose and the first full dose (C1D8); a minimum of 6 days should be maintained between doses thereafter. If a participant has received QW dosing for at least 6 cycles and has achieved an IMWG response category of PR or better persisting for at least 2 months, the dose interval will be changed from QW to Q2W (eg, beginning C7D1) (see Section 6.6.3).

Dose modifications may occur according to the guidelines described in Section 6.6.

The first doses of study intervention will be 12 mg (C1D1) and 32 mg (C1D4), which will serve as priming doses and will be administered on an inpatient basis. Participants are required to be hospitalized and monitored for CRS/ICANS for at least 2 days (~48 hours) beginning on C1D1, and for 1 day (~24 hours) for C1D4. Hospitalization up to 5 days from C1D1 to C1D5 inclusive may be considered.

The dose of elranatamab should be increased to 32 mg on C1D4 and to 76 mg on C1D8 as long as the participant meets the redosing criteria listed in Section 6.6.1. If a participant does not meet these criteria on C1D4 and C1D8, dosing should be deferred until the criteria are met.

For both the priming doses and first full dose (76 mg), premedication for CRS is required (see Section 6.5.1)

Each participant may receive study intervention until confirmed disease progression, unacceptable toxicity, withdrawal of consent, or study termination.

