## **Definition of baseline:**

No windowing will be applied when defining baseline. For example, the protocol requires safety assessments to be performed within 28 days prior to first dose; however, values outside this window will not be excluded when determining baseline assessments. Any deviations from the protocol specified window will be documented as protocol deviations. A separate definition of adequate baseline will be provided for disease assessment related efficacy endpoints.

For all endpoints, the last (measurable for efficacy) assessment performed on or prior to the date of the first dose of study intervention will serve as the baseline assessment. If there are no observations meeting these criteria, then baseline is considered missing. The screening EMD assessment will serve as the baseline assessment unless it is repeated by C1D1.

Participants who start treatment and discontinue from the study on the same day may have 2 different sets of data collected on Study Day 1 (one during study and one in the End of Treatment [EOT] visit). Data reported at the EOT visit are not eligible for baseline selection.

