## 3.5. Safety Endpoints

Safety endpoints will be summarized based on the on-treatment period unless otherwise specified.

On-treatment period is defined as the time from the first dose of study intervention through the minimum of [90 days after last dose, or (start day of new anticancer therapy -1 day)]. Anticancer therapy includes drug therapy, stem cell transplant, and radiation with curative intent; the start of new anticancer therapy after the first dose of study intervention is derived as outlined in Section 5.2.6. Adverse events occurring on the same day as the first dose of study intervention will be considered to have occurred during the on-treatment period. All other assessments which occur on the same day as the first dose of study intervention will be considered baseline assessments (see Section 3.4 for the definition of baseline).

Safety data collected after the on-treatment period as described above will be listed but not summarized.

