#### 5.2.11. Nominal and Unscheduled Visits

For all algorithms and analyses, visit labels as specified on the CRF will be used as the nominal timepoint (ie, assessment will not be slotted).

Unless otherwise specified, unscheduled assessments will not be displayed in summary tables by nominal visit/timepoint. Unscheduled assessments will be used when deriving baseline and worst case on-treatment for safety and PRO analyses (except where noted for baseline ECGs). Additionally, unscheduled assessments will be used for efficacy analyses (eg, defining date of progression/censoring, best overall response, date of last contact).

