#### 6.7.3. Laboratory Data

Laboratory results will be converted to International System of Units (Système International d'unités, SI) units which will be used for applying severity grades and for all summaries.

As described in Section 3.4, baseline will be defined as the last assessment performed on or prior to date of the first dose of study intervention. If there are multiple assessments that meet the baseline definition on the same day without the ability to determine which was truly last, then the worst grade will be assigned as the baseline grade.

Results collected as strict inequalities (eg, >10, <10) will be converted to numeric values adding or subtracting a factor of 0.001. Expressions of the form " $\geq$ " or " $\leq$ " will be converted to the end point. These numeric values will be evaluated for clinically significant abnormalities, but will not be included in calculations of summary statistics except for efficacy related laboratory results. Additional data handling rules for efficacy related laboratory data will be described in the programming plan.

Additionally, laboratory results will be programmatically classified according to NCI-CTCAE version 5.0 grade as appropriate. Non-numerical qualifiers will not be taken into consideration in the derivation of grade (eg, hypokalemia Grade 1 and Grade 2 are only distinguished by a non-numerical qualifier and therefore Grade 2 will not be derived). In summary statistics the number and percentage of participants corresponding to grades that only include non-quantitative criteria will be displayed as a blank or NA (not assessed) rather than 0. If there is any overlap between grade criteria (eg, CTCAE grading criteria for Creatinine Increased - a value can fall into one range based on comparison to ULN and another range based on comparison to baseline), the highest (worst) grade would be assigned to that record. Grade 5 is defined in the CTCAE criteria guidance as an event with an outcome of death. Since laboratory data does not collect an outcome, Grade 5 is not used when programmatically grading laboratory data. For laboratory tests without CTCAE grade definitions, results will be categorized as normal, abnormal, or not done.

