For calcium, CTCAE grading is based on Corrected Calcium and Ionized Calcium. Corrected Calcium is calculated from Albumin and Calcium as follows:

Corrected Calcium (mg/dL) = measured total calcium (mg/dL) – 0.8 [serum albumin (g/dL)-4]

Creatinine clearance is calculated as follows:

- Male: Creatinine Clearance = ((140 Age) / (Serum Creatinine)) \* (Weight / 0.814);
- Female: Creatinine Clearance (eGFR) = 0.85\* ((140 Age) / (Serum Creatinine)) \* (Weight / 0.814);

Note: the SI unit of Serum Creatinine is "micromol/L", the unit of weight is "Kg".

Abnormalities will be described using the worst grade overall. Worst case overall will be determined using laboratory results from scheduled and unscheduled visits. Several laboratory tests have bi-directional grading criteria defined so that both low (hypo) and high

(hyper) values can be graded separately. Each criterion will be summarized separately. In the cases where a value is graded as a Grade 1, 2, 3, or 4 for one of the directions, that value will also be assigned as a Grade 0 for the opposite direction for that test. For example, a value meeting the criteria for Grade 3 Hypercalcemia will be classified as a Grade 0 Hypocalcemia. For CTCAE terms that can be derived using one of several laboratory tests, the maximum postbaseline grade for a given participant and CTCAE term will be the maximum across all possible laboratory tests.

Additional laboratory results that are not part of CTCAE will be presented according to the following categories by scheduled timepoint as well as overall: below normal limit, within normal limits, and above normal limits. In the unlikely event that for a given participant, clinically significant abnormalities are noted in both directions (eg, > Upper Limit of Normal (ULN) and < Lower Limit of Normal [LLN]), then both abnormalities are counted.

The following summary tables will be created:

- Shift summary of laboratory parameters during the on-treatment period by maximum CTCAE grade;
- Shift summary of laboratory parameters from ≤ Grade 2 at baseline to ≥ Grade 3 postbaseline;
- Shift summary of laboratory test results with no CTCAE criteria by worst on treatment assessment.

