All laboratory test results will be presented in a data listing sorted by participant identifier, laboratory test, and date/time of collection. The CTCAE grades and the classifications relative to the laboratory reference ranges will be presented. Values outside laboratory normal ranges will be flagged where appropriate.

**Liver function tests:** Alanine aminotransferase (ALT), aspartate aminotransferase (AST), Alkaline Phosphatase (ALP), and total bilirubin (TBILI) are used to assess possible drug induced liver toxicity. The ratios of test results over the ULN will be calculated and classified for these 3 parameters during the on-treatment period.

Summary of liver function tests will include the following categories. The number and percentage of participants with each of the following during the on-treatment period will be summarized:

- ALT≥3×ULN, ALT≥5xULN, ALT≥10×ULN, ALT≥20×ULN;
- AST≥3×ULN, AST≥5xULN, AST≥10×ULN, AST≥20×ULN;
- (ALT or AST)≥3×ULN, (ALT or AST)≥5×ULN, (ALT or AST)≥10×ULN, (ALT or AST)≥20×ULN;
- TBILI≥2×ULN;

- Concurrent ALT≥3×ULN and TBILI≥2×ULN;
- ALT≥3×ULN and TBILI≥2×ULN at any timepoint;
- Concurrent AST≥3×ULN and TBILI≥2×ULN;
- AST≥3×ULN and TBILI≥2×ULN at any timepoint;
- Concurrent (ALT or AST)≥3×ULN and TBILI≥2×ULN;
- (ALT or AST)  $\geq$  3×ULN and TBILI  $\geq$  2×ULN at any timepoint;
- Concurrent (ALT or AST) >3×ULN and TBILI >2×ULN and ALP >2×ULN;
- (ALT or AST) >3×ULN and TBILI >2×ULN and ALP >2×ULN at any timepoint;
- Concurrent (ALT or AST) >3×ULN and TBILI >2×ULN and ALP <2×ULN or missing;
- (ALT or AST)≥3×ULN and TBILI≥2×ULN and ALP≤2×ULN or missing at any timepoint.

Concurrent measurements are those occurring on the same date.

Categories will be cumulative, ie, a participant with an elevation of AST $\geq$ 10×ULN will also appear in the categories  $\geq$ 5×ULN and  $\geq$ 3×ULN. Liver function elevation and possible Hy's Law cases will be summarized using frequency counts and percentages.

An evaluation of Drug-Induced Serious Hepatotoxicity (eDISH) plot will also be created, with different symbols for different cohorts, by graphically displaying:

- Peak serum ALT(/ULN) vs peak total bilirubin (/ULN) including reference lines at ALT=3×ULN and total bilirubin=2×ULN;
- Peak serum AST(/ULN) vs peak total bilirubin (/ULN) including reference lines at AST=3×ULN and total bilirubin=2×ULN.

In addition, the following listings of all TBILI, ALT, AST and ALP values will be provided:

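### The SAP sets baseline by calendar date, so a lab or PRO obtained after the first dose on C1D1 can become the baseline value (minor)

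*SAP*

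**What the plan says.** SAP 3.4 (Definition of baseline) gives one rule for all endpoints: the last "assessment performed on or prior to the date of the first dose of study intervention will serve as the baseline assessment". The only same-day data it excludes are those reported at an end-of-treatment visit.

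SAP 3.5 counts AEs on the first-dose date as on-treatment, then states: "All other assessments which occur on the same day as the first dose of study intervention will be considered baseline assessments".

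SAP 6.7.3 repeats the rule for laboratory data: "baseline will be defined as the last assessment performed on or prior to date of the first dose of study intervention". When several qualifying results fall on the same day "without the ability to determine which was truly last, then the worst grade will be assigned as the baseline grade".

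SAP 5.2.11 widens the pool: "Unscheduled assessments will be used when deriving baseline and worst case on-treatment for safety and PRO analyses". The PRO Analysis Set in SAP Section 4 likewise accepts a PRO obtained before or on the first dose.

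For AE dates, SAP 5.3.3.1 gives an imputation rule only for an onset date that is wholly missing. SAP 5.3.3.5 (Other Dates) replaces a missing day in a start date with the first of the month. SAP 5.3.3.3 handles partial death dates with a floor at the day after last contact.

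**The concern.** A baseline should describe the participant before exposure. The SAP rule compares calendar dates, so a result obtained some hours after the first priming dose still qualifies and, as the latest that day, takes precedence over the pre-dose result. SAP 3.5 then keeps it out of the on-treatment data.

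The protocol leaves room for such records. Protocol 6.1.1 says: "Participants are required to be hospitalized and monitored for CRS/ICANS for at least 2 days (~48 hours) beginning on C1D1". Protocol 8.2.6 allows unscheduled safety labs at any time. Protocol 8.1.4 prefers PROs before dosing but accepts completion up to the end of the visit.

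What is at stake is the worst on-treatment lab grade, the lab shift tables, in particular "Shift summary of laboratory parameters from ≤ Grade 2 at baseline to ≥ Grade 3 postbaseline", and PRO change from baseline. A day-1 lab toxicity could be recorded as a pre-existing abnormality.

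**Working it through.** **1. Is there a pre-dose condition elsewhere?** SAP 3.4, 3.5, 4, 5.2.11 and 6.7.3, read together, contain none. The protocol's conduct rules protect much of the data. Scheduled clinical assessments fall within the 72 hours before dosing, with noted exceptions (Protocol 1.3). Disease-response samples (8.1.1), physical and neurological examinations (8.2.2), dosing-day vital signs (8.2.3) and scheduled ECGs (8.2.4) come before the dose. Still exposed are unscheduled C1D1 labs, late C1D1 PROs and, conditionally, the scheduled 6-hour post-dose sBCMA sample.

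**2. Direction of the lab effect.** Let P be the pre-dose grade, Q the same-day post-dose grade and L the worst later on-treatment grade, each 0 to 4 (SAP 6.7.3 does not use Grade 5 for labs). That gives 5 × 5 × 5 = 125 patterns.

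| Rule | In the ≤2 to ≥3 table if | Patterns |
|---|---|---|
| Pre-dose baseline | P ≤ 2 and max(Q, L) ≥ 3 | 3 × (25 − 9) = 48 |
| SAP, order known | Q ≤ 2 and L ≥ 3 | 5 × 3 × 2 = 30 |
| SAP, order unknown | max(P, Q) ≤ 2 and L ≥ 3 | 3 × 3 × 2 = 18 |

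- Lost under either SAP reading: P ≤ 2, Q ≥ 3, any L, so 3 × 2 × 5 = 30. In 18 of these (L ≤ 2) the day-1 result was the only Grade ≥3 value. In the other 12 (L ≥ 3) the baseline itself has become Grade ≥3.
- Gained, order known: P ≥ 3, Q ≤ 2, L ≥ 3, so 2 × 3 × 2 = 12.
- Gained, order unknown: 0, because taking the worst grade can raise the baseline grade but never lower it.
- Check: 48 − 30 + 12 = 30, and 48 − 30 + 0 = 18.
- Worst on-treatment grade: L replaces max(Q, L). It is lower whenever Q > L, which is 10 of 25 (Q, L) pairs, times 5 values of P = 50. It is never higher.

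This takes the grades as given. SAP 6.7.3 notes that creatinine may also be graded against baseline, so for that test a displaced baseline could alter later grades too.

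**3. sBCMA (conditional).** The window for the 6-hour sample is ±36 minutes. The latest permitted draw is at 6 h 36 min, so it falls on the dosing date for any dose before 24:00 − 6:36 = 17:24. The earliest is at 5 h 24 min, so it never does for a dose after 24:00 − 5:24 = 18:36. Dose times are not given.

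**4. AE onset with a missing day (conditional).** Suppose SAP 5.3.3.5 is applied to AEs. An onset in the month of first dose is then dated to the 1st, which precedes treatment unless dosing was on the 1st. Assume dose dates uniform over 365 days and onset days uniform over the stated range. The share of missing-day AEs that lose treatment-emergent status is:

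- onset on days 0–6: 2219/2555 = 86.8%
- days 0–27: 5348/10220 = 52.3%
- days 0–89: 5373/32850 = 16.4%

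These figures are illustrative. The number of partial onset dates is unknown and may be very small, especially in the inpatient first week.

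**The case against.** The calendar-date rule is explicit and applied consistently, and date-based baselines are a common fallback when times are incomplete. Protocol conduct rules place nearly all scheduled data before the dose. For labs, only an unscheduled draw on one date is exposed, and no text says any was taken. Protocol 8.2.6 has clinically relevant lab changes recorded as AEs, and same-day AEs count as on-treatment. All lab values are listed with grades, hematology is repeated on C1D4, and hematology and chemistry on C1D8, C1D15 and C1D22. The one-way result needs the untimed tie-break, yet lab listings are "sorted by participant identifier, laboratory test, and date/time of collection". With times present, shifts go both ways. Equal-weight pattern counts are not effect sizes. PRO times may not exist, exploratory biomarkers are reported outside the CSR, and partial AE dates are a different matter from baseline.

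Most of this stands as a limit on size. The number of affected records is unknown and probably small, the tie-break result applies only to untimed labs, and the sBCMA and AE-date points depend on rules outside the baseline definition. None of it supplies the missing pre-dose condition. Nor are missing times a good reason to keep the rule for labs: Protocol 6.4 has dose date and time recorded in the CRF, and the SAP's own listing uses lab collection time. With times known, the current rule selects the post-dose draw because it is the last one.

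**Conclusion.** The rule is wrong as written, and the consequence is minor. Applied literally, it makes a post-dose C1D1 lab or PRO the baseline and removes such a lab from the on-treatment results. Worst on-treatment lab grades can then only stay the same or fall, with grades taken as given. For untimed results, the shift table from Grade ≤2 to ≥3 can only lose participants. For timed results it can also gain some.

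The effect is confined to the date of first dose. It does not reach ORR, the key secondary endpoint or scheduled pre-dose labs. The sBCMA point holds only if the separate biomarker report, which is not among the documents, sets no baseline rule of its own. The AE-date point holds only if SAP 5.3.3.5 is used for AEs; what is certain is that SAP 5.3.3.1 has no rule for a missing day. AEs not counted as treatment-emergent remain flagged in listings. No main conclusion of the trial is at risk.

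**What to change.** 1. In SAP 3.4, 3.5 and 6.7.3, define baseline as the last non-missing assessment before the date and time of first dose. Treat same-day assessments known to be post-dose, by time or by nominal label, as post-baseline.
2. Where no time is available, keep the scheduled C1D1 record as baseline, including the C1D1 PRO, unless its label says post-dose.
3. Do not use an untimed unscheduled same-day lab as baseline when a scheduled pre-dose value exists, and leave it out of the worst-grade tie-break in 6.7.3.
4. Align the PRO Analysis Set wording in Section 4.
5. Separately, add to 5.3.3.1: if the onset day is missing and the month and year match those of first dose, impute the first-dose date unless the AE stop date is earlier.

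The cost is SAP wording and minor programming on data already collected. SAP 5.2.7 mentions only completion dates for PROs, so item 2 ensures that no PRO baseline is lost for lack of a time. It also means that a late but untimed C1D1 PRO remains baseline, a limitation worth stating. Lab shift, PRO change and TEAE counts may move slightly.

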## 3.5. Safety Endpoints

Safety endpoints will be summarized based on the on-treatment period unless otherwise specified.

On-treatment period is defined as the time from the first dose of study intervention through the minimum of [90 days after last dose, or (start day of new anticancer therapy -1 day)]. Anticancer therapy includes drug therapy, stem cell transplant, and radiation with curative intent; the start of new anticancer therapy after the first dose of study intervention is derived as outlined in Section 5.2.6. Adverse events occurring on the same day as the first dose of study intervention will be considered to have occurred during the on-treatment period. All other assessments which occur on the same day as the first dose of study intervention will be considered baseline assessments (see Section 3.4 for the definition of baseline).

Safety data collected after the on-treatment period as described above will be listed but not summarized.

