8.3.1. Time Period and Frequency for Collecting AE and SAE Information

The time period for actively eliciting and collecting AEs and SAEs ("active collection period") for each participant begins from the time the participant provides informed consent,

which is obtained before the participant's participation in the study (ie, before undergoing any study-related procedure and/or receiving study intervention), through and including a minimum of 90 calendar days, except as indicated below, after the last administration of the study intervention. NOTE, as indicated in Section 8.3.1.2: If a participant begins a new anticancer therapy, the recording period for nonserious AEs ends at the time the new treatment is started; however, SAEs must continue to be recorded on the CRF during the above-indicated active collection period.

Only SAEs will be actively elicited and collected after completion of the active collection period described above. The SAEs will be reported to Pfizer Safety on the CT SAE Report Form only if considered reasonably related to elranatamab.

Follow-up by the investigator continues throughout and after the active collection period and until the AE or SAE or its sequelae resolve or stabilize at a level acceptable to the investigator and Pfizer concurs with that assessment.

For participants who are screen failures, the active collection period ends when screen failure status is determined.

If the participant withdraws from the study and also withdraws consent for the collection of future information, the active collection period ends when consent is withdrawn.

If a participant definitively discontinues or temporarily discontinues study intervention because of an AE or SAE, the AE or SAE must be recorded on the CRF and the SAE reported using the Electronic Data Collection Tool.

Investigators are not obligated to actively seek AEs or SAEs after the participant has concluded study participation. However, if the investigator learns of any SAE, including a death, at any time after a participant has completed the study, and he/she considers the event to be reasonably related to the study intervention, the investigator must promptly report the SAE to Pfizer using the CT SAE Report Form.

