## 3.5.1. Adverse Events

An adverse event is considered treatment-emergent relative to study intervention if the adverse event start date is during the on-treatment period (including on the date of first dose).

AEs will be as characterized by type, severity, timing, seriousness, and relationship to study intervention.

AEs (except CRS and ICANS) will be graded by the investigator according to the NCI CTCAE version 5.0. CRS and ICANS will be graded by the investigator according to the ASTCT criteria. All AEs will be coded using the most current version of Medical Dictionary for Regulatory Activities (MedDRA).

TEAEs leading to dose interruption or dose reduction will be derived from the exposure CRF (dose adjustment reason as adverse event and actual dose taken of 0 for interruption and >0 for reduction) and then linked programmatically to the adverse event CRF by the AE identifier.

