## 5.3.3.4. Date of Start of New Anticancer Therapy

Incomplete dates for start date of new anticancer therapy (drug therapy, radiation with curative intent, transplant) will be imputed as follows and will be used for determining censoring dates for efficacy analyses and in the derivation of the end of the on-treatment period. PD date below refers to PD date by investigator assessment. If the imputation results in an end date prior to the imputed start date, then the imputed start date should be set to the end date.

- The end date of new anticancer therapy will be included in the imputations for start date of new anticancer therapy. If the end date of new anticancer therapy is
  - completely missing then it will be ignored in the imputations below;
  - partially missing with only year (YYYY) available then the imputations below will consider 31DECYYYY as the end date of the new anticancer therapy;
  - partially missing with only month and year available then the imputations below will consider the last day of the month for MMMYYYY as the end date of the new anticancer therapy.
- For participants who have not discontinued study intervention at the analysis cutoff date, last dose of study treatment is set to the analysis cutoff date in the imputations below.
- If the start date of new anticancer therapy is completely or partially missing, then the imputed start date of new anticancer therapy is derived as follows:
  - Start date of new anticancer therapy is completely missing
    - Imputed start date = min [max(PD date + 1, last dose of study intervention + 1), end date of new anticancer therapy]
  - Only year (YYYY) for start of anticancer therapy is available
    - IF YYYY < Year of min [max(PD date + 1, last dose of study intervention + 1), end date of new anticancer therapy]

THEN imputed start date = 31DECYYYY;

• ELSE IF YYYY = Year of min [max(PD date + 1, last dose of study intervention + 1), end date of new anticancer therapy]

THEN imputed start date = min [max(PD date + 1, last dose of study intervention + 1), end date of new anticancer therapy]

• ELSE IF YYYY > Year of min [max(PD date + 1, last dose of study intervention + 1), end date of new anticancer therapy]

THEN imputed start date = 01JANYYYY

- Both Year (YYYY) and Month (MMM) for start of anticancer therapy are available
  - IF YYYY = Year of min [max(PD date + 1, last dose of study intervention + 1), end date of new anticancer therapy], AND

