#### 6.7.1. Adverse Events

All analyses will be based on treatment emergent adverse events (TEAEs) unless otherwise specified. Treatment emergent is defined in Section 3.5. AEs not considered treatment emergent will be flagged in data listings. Summaries of TEAEs due to COVID-19 may be produced if appropriate.

A high-level summary of adverse events (all causality and treatment-related, separately) will include the number and percent of participants with:

- Any TEAEs;
- Serious TEAEs;
- Grade 3-4 TEAEs;
- Grade 5 TEAEs;
- TEAEs leading to dose interruptions;
- TEAEs leading to dose reductions;
- TEAEs leading to dose interruptions or reductions;
- TEAEs leading to permanent discontinuation of study intervention;
- CRS;

- ICANS;
- Peripheral neuropathy.

Seriousness, toxicity grade, and withdrawal from drug are as reported by the investigator on the adverse event CRF.

An event will be considered treatment-related if the investigator considered the event as related to the study drug or if relationship is missing.

For all the AE summaries by SOC and PT, or PT only, the following cytopenias will be clustered. Each participant will be counted only once within each SOC and clustered terms. However, the number of total events will be based on the individual PTs.

- Thrombocytopenia (PT=Thrombocytopenia; Platelet count decreased);
- Anaemia (PT=Anaemia; Haemoglobin decreased, Red blood cell count decreased, Haematocrit decreased, Normochromic anaemia, Normocytic anaemia, Normochromic normocytic anaemia);
- Neutropenia (PT=Neutropenia; Neutrophil count decreased, Neutrophil percentage decreased, Cyclic neutropenia, Agranulocytosis, Granulocytopenia, Granulocyte count decreased);
- Leukopenia (PT=Leukopenia; White blood cell count decreased);
- Lymphopenia (PT=Lymphopenia; Lymphocyte count decreased, Lymphocyte percentage decreased, CD4 lymphocytes decreased, CD4 lymphocyte percentage decreased, CD8 lymphocytes decreased, CD8 lymphocyte percentage decreased).

Summaries by SOC and PT by alphabetical order for SOC and by descending order of frequency for PT in two cohorts combined will be provided for:

- TEAEs (all causality and treatment-related);
- TEAEs by maximum severity grade (all causality and treatment-related);
- TEAEs with Grade 3-4 (all causality and treatment-related);
- TEAEs leading to death (all causality and treatment-related);
- TEAEs leading to dose interruptions (all causality);
- TEAEs leading to dose reductions (all causality);

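### SAEs that start after a switch to new anticancer therapy, within 90 days of last dose, are collected but left out of the safety tables; add one supplementary summary of the treatment-related ones

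*SAP*

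**What the plan says.** **Collection.** Protocol 8.3.1 sets the active collection period to run at least 90 days past the last dose. When new anticancer therapy starts, recording of nonserious AEs stops, but "SAEs must continue to be recorded on the CRF during the above-indicated active collection period". Protocol 8.3.1.1 likewise keeps SAE reporting to sponsor safety going whatever treatment intervenes. The Amendment 5 summary gives late immune-related neurologic events as one reason for lengthening the period to 90 days.

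**Analysis.** SAP 3.5 ends the on-treatment period at the smaller of "90 days after last dose, or (start day of new anticancer therapy -1 day". SAP 3.5.1 then defines a TEAE by onset: "An adverse event is considered treatment-emergent relative to study intervention if the adverse event start date is during the on-treatment period". SAP 6.7.1 applies this to every AE table: "All analyses will be based on treatment emergent adverse events (TEAEs) unless otherwise specified". SAP 6.7.1.1 (AESIs) states no exception. Whatever falls outside the window is covered by this sentence of SAP 3.5: "Safety data collected after the on-treatment period as described above will be listed but not summarized".

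**Missing therapy dates.** If the start date of the new therapy is completely missing, SAP 5.3.3.4 uses "Imputed start date = min [max(PD date + 1, last dose of study intervention + 1), end date of new anticancer therapy". That imputed date serves for efficacy censoring "and in the derivation of the end of the on-treatment period".

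**Relatedness.** SAP 6.7.1: "An event will be considered treatment-related if the investigator considered the event as related to the study drug or if relationship is missing".

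**Deaths.** SAP 6.7.2 separately tabulates deaths at any time and within 90 days of last dose, with primary reason. It makes no cut at new therapy.

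**The concern.** The collection rule and the tabulation rule use different windows for anyone who switches therapy early. The protocol extended follow-up partly to catch delayed neurologic toxicity, and Protocol 8.3.11 treats peripheral neuropathy including GBS as an important potential risk. For a participant who starts a new regimen soon after stopping elranatamab, most of the extended window can drop out of the tables. A late serious neuropathy that the investigator attributes to elranatamab would then appear only as a flagged line in a listing. It would not be in the serious TEAE, serious AESI or treatment-related tables.

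What is at stake is how complete the reported safety profile is. Efficacy is not affected. Safety monitoring is not shown to be affected either, because the SAEs still reach sponsor safety and the E-DMC reviews cumulative safety data.

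**Working it through.** The plan gives no figure on this point to reproduce. The check traces the definitions and then measures how much of the window is lost.

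**Step 1: follow one event.** Let day 0 be the last dose and let new therapy start on day g, with g from 1 to 90. Take an SAE with onset between day g and day 90.

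- It is recorded and reported (Protocol 8.3.1, 8.3.1.1 and 8.3.1.2).
- The on-treatment period ended on day g − 1 (SAP 3.5), so the event is not a TEAE (SAP 3.5.1).
- It is therefore absent from the serious, Grade 5 and treatment-related TEAE tables (SAP 6.7.1) and, through the same general rule, from the AESI tables (SAP 6.7.1.1).
- It is listed and flagged as not treatment-emergent (SAP 3.5 and 6.7.1).

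An SAE starting on day g itself is also excluded. An event with onset before day g stays in the tables. Nonserious AEs play no part, because their recording stops at day g.

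**Step 2: share of the post-dose window omitted.** The tables keep g − 1 of the 90 post-dose days, so they omit 90 − (g − 1) = 91 − g days. The values of g are assumptions; the documents give no distribution of time to next therapy.

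| New therapy starts on day g | Days omitted (91 − g) | Share of 90 days |
|---|---|---|
| 1 | 90 | 100% |
| 14 | 77 | 85.6% |
| 28 | 63 | 70.0% |
| 42 | 49 | 54.4% |
| 60 | 31 | 34.4% |
| 91 or later | 0 | 0% |

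**Step 3: the extreme case under the plan's own rule.** Suppose the therapy start date is completely missing and investigator-assessed PD fell on or before the last dose. Then max(PD + 1, last dose + 1) = last dose + 1. Taking the minimum with the therapy end date can only move this earlier. So g is at most 1, and all 90 post-dose days are omitted.

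**Step 4: effect of one uncounted participant.** The denominators are the enrolled and treated numbers in Protocol 9.2: 123 in Cohort A and 64 in Cohort B, 187 in total.

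- Both cohorts: 1/187 = 0.53%
- Cohort A: 1/123 = 0.81%
- Cohort B: 1/64 = 1.56%

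Each is the most one participant can add to a table row. Someone already counted in that row for an earlier event adds nothing.

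**The case against.** The case for leaving the plan alone is reasonable.

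- **There is no conflict between the documents.** The protocol governs collection and reporting. Neither Protocol 8.3.1 nor 9.4.5.1 requires SAEs after a switch to be tabulated. This stands, and it is why the point is not graded as an error.
- **The cut has a good purpose.** It keeps toxicity of the next regimen out of the elranatamab tables, and Protocol 8.3.11 itself names IMiDs and proteasome inhibitors as causes of neuropathy. This also stands. It argues for keeping the main tables as they are and for limiting any addition to treatment-related events.
- **Much of the information appears elsewhere.** The events are in listings, deaths within 90 days are tabulated with primary reason, and SAP 2 allows further non-efficacy analyses. This is partly right. What the death table does not give is the Grade 5 event's preferred term and relatedness, and nonfatal SAEs have no table at all. An analysis that is permitted but not specified can be added or omitted after the data are seen.
- **The size is unknown.** The percentages in Step 2 measure calendar days and not events, and the extreme case needs an unusual pattern of missing data. Both are true.
- **Attribution is uncertain after a switch.** A missing relationship counts as related, and Protocol 10.3.3 handles unknown causality as related for reporting. The added table could therefore include events that nobody positively attributed to elranatamab. This is a real limitation, but showing those events separately makes it visible.

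**Conclusion.** The concern holds as a low-priority, cheap improvement. Under the stated rules, a serious event attributed to elranatamab that starts on or after new therapy and within 90 days of last dose is collected and listed but counted in none of the AE tables.

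The definitional trace needs no assumptions. The share of the window lost depends on the assumed time to next therapy, from 34% at day 60 to 86% at day 14. The number of participants or events affected cannot be obtained from the documents and may be zero. The gap matters most for nonfatal treatment-related SAEs, since fatal cases within the window still reach the death table.

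**What to change.** Leave the TEAE tables as the main analysis. Add to SAP 6.7.1 and 6.7.1.1 one supplementary summary covering first dose through 90 days after last dose, regardless of new anticancer therapy, with three rows:

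1. treatment-related SAEs;
2. treatment-related serious peripheral neuropathy/GBS AESIs;
3. treatment-related Grade 5 events.

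Flag events with onset on or after new therapy, and mark those where the therapy start date was imputed. Show separately the events counted as related only because the relationship is missing or, where the CRF records it, unknown.

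Do not add all-causality rows. They would bring in toxicity of the next regimen, and also fatal progression, which Protocol 10.3.2 has recorded as a Grade 5 SAE.

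The cost is SAP wording and one flagged table from data already on the CRF. Two limits remain: some added events may be due to the next regimen, and late nonserious neuropathy after a switch stays unseen because it is not collected.
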